10. DEVIATIONS FROM ANALYSIS DESCRIBED IN THE PROTOCOL

The following update has been made from the planned analysis defined in the protocol to align the safety analysis plan as defined in the TA799-007 study.

- In the protocol, TEAE is defined as all AEs occurring after first dose of trial medication and up to the 4 weeks follow-up visit. However, for the safety analysis, TEAE will be defined as any adverse events that started on or after the first dose of trial medication (i.e. no longer depends on 4 weeks follow-up visit).

There is one deviation from the planned analysis described in the protocol. According to the protocol, the primary endpoint AESIs are to be derived based on SMQ or CQs. Sponsor issued NTF (See [Appendix 4: Addendum to Statistical Analysis Plan](#)), to clarify that AESI will be identified by using the investigator's assessment, reported in eCRF for analysis.

In addition, the following list contains typographical error (typo) corrections from the protocol that have been made to this SAP for clarity:

- The protocol refers to 'change in absolute absorption'. It is clarified in SAP that this refers to 'absolute change from baseline' in comparison to 'relative change in absorption'. Note: This SAP uses 'absolute change from baseline' and 'change from baseline' interchangeably.
- One of the secondary efficacy endpoints defined in the protocol is 'clinical responder at Week 52' but unlike the protocol synopsis and Section 1.5.2.2 of the protocol, Section 7.1.2 of the protocol indicated Week 48 instead of Week 52. This typo has been corrected to Week 52 in this SAP.
- One of the efficacy endpoints defined in the protocol is 'change in dietary intake of wet weight, energy, macronutrients, fluid, electrolytes (sodium, potassium, calcium, and magnesium) from baseline at Week 4 and Week 48', but this 'fluid' is a part of weight as oral fluid; hence, this text, 'fluid', is omitted in this SAP.
- One of the efficacy endpoints defined in the protocol is "change in fecal excretion of wet weight, energy, macronutrients, fluid and electrolytes (sodium, potassium, calcium, and magnesium) from baseline at Week 4 and Week 48", but this "fluid" is a part of wet weight (urine), which has already been covered by urine output as a part of the secondary efficacy endpoint; hence, the text, 'fluid', is omitted in this SAP.
- The protocol states the sensitivity analysis excluding subjects missing more than 20% of the planned injections prior to the time of analysis, and the number of injections leading to exclusion are to be 1 at Week 4, 6 at Week 24, and 11 at Week 52, but this text has been corrected to "... 1 at Week 4, 5 at Week 24, and 10 at Week 48", respectively, in order to exclude subjects missing more than 20% of the planned injections prior to the corresponding analysis timepoint.
- One of the exploratory endpoints defined in the protocol stated "change in body weight from baseline at Week 24 and Week 52", but the protocol synopsis refers to "Week 48". This has been consistently referred to as Week 48 in the SAP for the efficacy endpoint, although the change in body weight from baseline to Week 52 will be also summarized for safety analyses.
- One of secondary endpoints related to PRO is 'PGIC at Week 24 and Week 52' but unlike the protocol synopsis and Section 7.1.2, Section 1.5.2.2 of the protocol indicated as 'change in PGIC' where it should only be referred as 'PGIC'. This typo has been corrected in this SAP.
- SBS-IF-TI-QOL data collection has been removed from baseline according to the protocol amendment version 3 dated 03SEP2021, hence the change from baseline analysis defined as the endpoint has been updated to 'observed'.

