5.1.10.7 Adverse Events of Special Interest

The handling of AESIs is described in detail in Section 6.2.2; special reporting requirements apply (Section 6.3.4). When documenting an AE as per Section 5.1.10.6, the Investigator will assess if the AE is an AESI.

In this trial, AESIs are

- Injection site reactions
- GI obstructions
- Gallbladder, biliary and pancreatic disease
- Fluid overload
- Colorectal polyps
- Malignancies

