Grade 2	Moderate with noticeable skin change from scratching (e.g., excoriation). Oral therapy indicated
Grade 3	Widespread and resulting in treatment interruption
Induration	
Grade 1	Mild induration with skin able to slide and pinch up
Grade 2	Unable to pinch up skin but still slides
Grade 3	Severe, unable to slide or pinch, potentially limiting activity of daily living and consideration of treatment interruption
Erythema	
Grade 1	Mild, <2.5 cm
Grade 2	Moderate, 2.5–5 cm
Grade 3	Severe, >5 cm
Bruising	
Grade 1	Mild, <2.5 cm
Grade 2	Moderate, 2.5–5 cm
Grade 3	Severe, >5 cm

NCI-CTCAE, National Cancer Institute – Common Terminology Criteria for Adverse Events

Gastrointestinal Obstruction

Any GI obstructions will be treated by the Investigator according to the Investigator's judgment and carefully followed up.

Gallbladder, Biliary and Pancreatic Disease

These should be monitored by symptoms, liver enzymes (ALT, AST, GGT, alkaline phosphatase), bilirubin, lipase and amylase and subjects should be treated according to the Investigator's judgment.

Fluid Overload

Subjects will be monitored closely for signs and symptoms related to fluid overload, e.g., edema, due to increased absorption. The Investigator will document cases of substantial fluid overload and manage as per clinical practice for the subject accordingly.

Colorectal Polyps

Where deemed anatomically feasible by the Investigator, two gastroduodenoscopies and colonoscopies or colonographies will be done during the course of the trial, one before enrolment and one at the end of the trial. Any polyps found during colonoscopies must be removed, and the histology documented in the source documents and eCRF.

Malignancies

For any subject with a malignancy identified during the course of the trial, a thorough medical history will be taken and documented (e.g., smoking history for lung cancer). Information on type of malignancy, histological type and grading will be collected. The IMP treatment will be discontinued, and the subject will be closely followed up by the Investigator.

Once the clinical database containing all AEs is available, potential AESIs will be identified using the following algorithmic standardized Medical Dictionary for Regulatory Activities (MedDRA) queries (including Standardized MedDRA Queries (SMQs)):

- Standardized MedDRA Queries Functional, inflammatory and gallstone related biliary disorders

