- Standardized MedDRA Queries GI perforation, ulceration, hemorrhage or obstruction
- Standardized MedDRA Queries Malignancies

In the absence of related SMQs, customer queries (CQs) will be set up from the Sponsor-defined list of preferred terms (PTs) as listed in the Statistical Analysis Plan (SAP).

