9.8.2 ADVERSE EVENTS

AEs that started on or after the first trial treatment will be categorized as TEAEs; whereas AEs that started on or after signing ICF but prior to first trial treatment will be categorized as pre-treatment AEs.

TEAEs reported as definitely, probably, or possibly related to the trial treatment will be deemed as trial treatment-related TEAEs for the purpose of reporting.

On-treatment AEs will be defined as any AE recorded in the trial database, started on or after the first trial treatment until 4 weeks from the last trial treatment (i.e., date of last trial treatment +28 days inclusive).

AESI will be programmatically derived based on [Appendix 3: Sponsor-Defined List of Preferred Terms](#). As ongoing pharmacovigilance could reveal new relevant Standardize MedDRA Queries (SMQs) or Customer Queries (CQs), the final selection will be determined at the data review meeting prior to database lock. The additional changes to this plan can be found in [Appendix 4: Addendum to Statistical Analysis Plan](#).

All AEs will be coded using MedDRA version 24.0 or higher.

An overall summary of AEs will be presented, which will include the incidence (%) of subjects with at least one pre-treatment AE, TEAE, treatment-emergent serious adverse event (TESAE), treatment-emergent AESI (programmatically derived as described above), trial treatment-related TEAE, trial treatment-related TESAE, TEAE leading to trial treatment dose increased, dose reduction of trial treatment, dose interruption of trial treatment, permanent discontinuation of trial treatment, not entering 4 weeks of safety follow-up, follow-up discontinuation, AE leading to death, and on-treatment AE along with the number of events.

The incidence (%) of subjects experiencing AEs for the following categories will be further summarized by SOC and PT in separate tables:

- TEAE

- Treatment-emergent AESI (programmatically derived)
- Trial treatment-related TEAE
- TEAE by severity
- On-treatment AE
- TESAE
- Non-serious TEAE
- Trial treatment-related TESAE

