Gallbladder, biliary and pancreatic disease	PT: Hypercholia	
Gallbladder, biliary and pancreatic disease	PT: Liver disorder	
Gallbladder, biliary and pancreatic disease	PT: Oedema due to hepatic disease	
Gallbladder, biliary and pancreatic disease	PT: Bilirubin excretion disorder	
Gallbladder, biliary and pancreatic disease	PT: Hepatic function abnormal	

AESI Category	SMQ or CQ	SMQ Scope
Gallbladder, biliary and pancreatic disease	PT: Hypertransaminasaemia	
Gallbladder, biliary and pancreatic disease	PT: Cholestatic liver injury	
Gallbladder, biliary and pancreatic disease	PT: Drug-induced liver injury	
Gallbladder, biliary and pancreatic disease	PT: Hepatitis	
Gallbladder, biliary and pancreatic disease	PT: Hepatitis acute	
Gallbladder, biliary and pancreatic disease	PT: Hepatitis toxic	
Gallbladder, biliary and pancreatic disease	PT: Hepatocellular injury	
Gallbladder, biliary and pancreatic disease	PT: Hepatotoxicity	
Gallbladder, biliary and pancreatic disease	PT: Liver injury	
Gallbladder, biliary and pancreatic disease	PT: Mixed liver injury	
Gallbladder, biliary and pancreatic disease	PT: Non-alcoholic steatohepatitis	
Gallbladder, biliary and pancreatic disease	PT: Nonalcoholic fatty liver disease	
Gallbladder, biliary and pancreatic disease	PT: Steatohepatitis	
Gastrointestinal obstructions	SMQ Gastrointestinal obstruction	Narrow
Gastrointestinal obstructions	SMQ Gastrointestinal perforation, ulcer, haemorrhage, obstruction non-specific findings/procedures	Broad+Narrow
Gastrointestinal obstructions	PT: Intestinal obstruction	
Malignancies	SMQ Malignancy related conditions	Narrow
Malignancies	SMQ Malignancy related therapeutic and diagnostic procedures	Narrow
Malignancies	SMQ Malignant or unspecified tumours	Narrow
Colorectal polyps	PT: Anal polyp	
Colorectal polyps	PT: Anorectal haemangioma	
Colorectal polyps	PT: Appendix adenoma	
Colorectal polyps	PT: Benign anorectal neoplasm	
Colorectal polyps	PT: Benign duodenal neoplasm	
Colorectal polyps	PT: Benign gastric neoplasm	
Colorectal polyps	PT: Benign gastrointestinal neoplasm	
Colorectal polyps	PT: Benign mesenteric neoplasm	
Colorectal polyps	PT: Benign neoplasm of islets of Langerhans	
Colorectal polyps	PT: Benign oesophageal neoplasm	
Colorectal polyps	PT: Benign pancreatic neoplasm	
Colorectal polyps	PT: Benign peritoneal neoplasm	
Colorectal polyps	PT: Benign small intestinal neoplasm	
Colorectal polyps	PT: Colon adenoma	
Colorectal polyps	PT: Duodenal polyp	

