Injection site reactions	PT: Injection site paraesthesia	
Injection site reactions	PT: Injection site phlebitis	
Injection site reactions	PT: Injection site photosensitivity reaction	
Injection site reactions	PT: Injection site plaque	
Injection site reactions	PT: Injection site pruritus	
Injection site reactions	PT: Injection site pustule	
Injection site reactions	PT: Injection site rash	
Injection site reactions	PT: Injection site reaction	
Injection site reactions	PT: Injection site recall reaction	
Injection site reactions	PT: Injection site scar	
Injection site reactions	PT: Injection site swelling	
Injection site reactions	PT: Injection site telangiectasia	
Injection site reactions	PT: Injection site thrombosis	
Injection site reactions	PT: Injection site ulcer	
Injection site reactions	PT: Injection site urticaria	
Injection site reactions	PT: Injection site vasculitis	
Injection site reactions	PT: Injection site vesicles	
Injection site reactions	PT: Injection site warmth	
Injection site reactions	PT: Injection site hypoaesthesia	
Injection site reactions	PT: Application site hypersensitivity	
Injection site reactions	PT: Immediate post-injection reaction	
Injection site reactions	PT: Skin reaction	
Injection site reactions	PT: Anaphylactic reaction	
Injection site reactions	PT: Anaphylactic shock	
Injection site reactions	PT: Anaphylactoid reaction	
Injection site reactions	PT: Anaphylactoid shock	
Fluid overload	PT: Fluid overload	
Fluid overload	PT: Hypervolaemia	
Fluid overload	PT: Oedema	

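### A note to file puts the investigator's flag in place of SMQ/CQ derivation for the primary AESI endpoint, and the SAP does not say whether the term search is kept even as support

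*SAP*

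**What the plan says.** **Protocol.** When an adverse event is documented, "the Investigator will assess if the AE is an AESI" (5.1.10.7). Section 6.2.2 adds a second source, applied once the whole AE database exists: "potential AESIs will be identified using the following algorithmic standardized Medical Dictionary for Regulatory Activities (MedDRA) queries". Where no SMQ fits, "customer queries (CQs) will be set up from the Sponsor-defined list of preferred terms" given in the SAP. Section 7.6.1 plans summaries for SMQs and CQs in the same style as those for TEAEs.

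**SAP body.** Section 7.1 keeps AESIs as a primary endpoint, and Section 2 says the analysis follows protocol version 4 for all subjects. Section 9.8.2 states that "AESI will be programmatically derived based on" Appendix 3. It uses the same programmatic label in the overall AE summary and in the list of SOC/PT tables.

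**SAP 10 and the note to file.** Section 10 reads the protocol as deriving primary-endpoint AESIs from SMQs or CQs. It then declares one deviation: the sponsor issued a note "to clarify that AESI will be identified by using the investigator", meaning the assessment recorded in the eCRF. Section 2 dates the note 6 December 2022, after SAP version 2.0 (22 July 2022) and ahead of the second interim analysis. Section 2 also gives the note precedence over every other SAP section and over the mock tables. Section 9.8.2 points to Appendix 4 twice for changes, but Appendix 4 contains only a reference to the note, not its text.

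**The concern.** The flag and the search do different jobs. The flag records what one investigator, in an open-label trial, chose to label. The search applies the same term list to every event, whoever reported it. If only the flag feeds the AESI tables, an event that belongs to a category but was not labelled drops out of a primary endpoint. Nothing in the planned output would then show how often that happened.

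SAP 10 describes the change as a clarification, yet in the same paragraph calls it a deviation. It gives no reason for it, although the TEAE change just above it does get one (alignment with TA799-007). It is also silent on the SMQ and CQ summaries planned in protocol 7.6.1.

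**Working it through.** There is no sample size, power or event figure to reproduce. The check is a comparison of passages, followed by one calculation for scale.

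**1. Which rule governs?**
- Protocol 5.1.10.7 with 6.2.2: investigator flag plus term search.
- SAP 9.8.2: programmatic derivation from Appendix 3.
- SAP 10: investigator assessment from the eCRF, declared as a deviation from SMQ/CQ derivation.
- SAP 2: the note overrides conflicting SAP text.

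The investigator flag therefore defines the AESI analysis, and the label in 9.8.2 is left over. Neither SAP 10 nor Appendix 4 says what becomes of the Appendix 3 search or of the protocol 7.6.1 summaries.

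**2. Can the two methods give different answers?** Yes.
- *Search wider than flag.* Protocol 6.2.2 asks investigators to document substantial fluid overload, and 4.5 ties the required AESI report to significant overload with decompensation. Appendix 3 counts any event coded to the preferred term Oedema. Mild oedema not called fluid overload is found by the search and may not be flagged.
- *Search wider in the biliary category.* Appendix 3 includes general liver terms there (hepatitis, drug-induced liver injury, fatty liver disease and others). Protocol 6.6.2 says abnormal liver tests are common in patients dependent on parenteral nutrition.
- *Terms filed under a category whose name they do not fit.* "PT: Benign oesophageal neoplasm" appears under colorectal polyps, as do gastric and pancreatic lesions. "PT: Anaphylactic shock" and three related anaphylactic or anaphylactoid terms appear under injection site reactions, which protocol 6.2.2 describes by local signs.

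**3. Scale.** Inputs: 2 subjects enrolled in France and 7 in Belgium (SAP 2), so n = 2 + 7 = 9. The SAP does not state the size of the Safety Analysis Set, so n = 9 is an assumption. Incidence = subjects with at least one event in the category / n, with exact Clopper-Pearson 95% limits:

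| Subjects in category | Incidence | 95% CI |
|---|---|---|
| 0 of 9 | 0% | 0 to 33.6% |
| 1 of 9 | 11.1% | 0.3 to 48.2% |
| 2 of 9 | 22.2% | 2.8 to 60.0% |

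One subject classified differently moves a category by 1/9 = 11.1 points. SAP 9.8.2 counts a subject once per category, so a further unflagged event in a subject already counted moves the incidence by 0.

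**The case against.** The strongest reply is that the plan has already settled this. The note has explicit precedence, 9.8.2 sends the reader to Appendix 4, SAP 10 discloses the deviation, and protocol 7.9 requires the final report to explain it. All of that stands. A reader might infer that the SAP gives two competing instructions; the precedence rule in SAP 2 rules that out.

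Three other stronger readings are tempting and are not supported:
- *That the flag is now the only source and the search has been abandoned.* Replacement is the natural reading of SAP 10, but the note itself is not reproduced and SAP 10 does not exclude a supportive search. Nor is the flag new: the protocol already had it, and its search finds only potential AESIs.
- *That unflagged events are lost from the report.* They can leave the AESI table and listing only. TEAEs are still tabulated by SOC and PT and by severity, all AEs are listed, and AEs are themselves a primary endpoint. With nine subjects a reader could compare the listing with Appendix 3 by hand.
- *That the change was prompted by interim results.* The documents give its timing but no reason for it, and timing alone does not show this.

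It can also be said that grouping terms is a pharmacovigilance choice and that 9.8.2 leaves the final query selection to the data review meeting before database lock. That is fair, and it makes that meeting the natural place for any regrouping.

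**Conclusion.** The point holds in a limited form. For a primary safety endpoint, a note to file puts investigator assessment in place of SMQ/CQ derivation. The SAP neither reproduces the note nor says whether the protocol's second source is kept in any form. The remaining programmatic wording in 9.8.2 is an editing fault.

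The possible effect is 11.1 percentage points per category for each subject the two methods classify differently, assuming all 9 enrolled subjects are in the safety set. How many subjects would differ cannot be known from the documents. This is worth correcting because it is cheap and restores a summary the protocol planned; it does not invalidate the AESI analysis.

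**What to change.** 1. Keep the investigator-flagged AESI table as the main one, as the note directs.
2. Add the Appendix 3 SMQ/CQ-derived AESI table as a supportive analysis, with a listing of events that one method captures and the other does not.
3. At the pre-lock data review, examine the Appendix 3 groupings so that anaphylaxis terms are not counted as injection site reactions and oesophageal, gastric and pancreatic lesions are not counted as colorectal polyps. Look at the liver terms at the same time. Document each change and its reason.
4. Change the 9.8.2 text and table labels to match SAP 10, put the note's text in Appendix 4, give the reason for the change, and state whether the protocol 7.6.1 summaries are kept.

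Cost: one table, one listing and text edits, with no new data. The supportive counts may exceed the flagged counts, particularly in the biliary category because of its liver terms, so the table needs a footnote saying so.

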11. PROGRAMMING SPECIFICATIONS

All outputs will be produced using SAS version 9.4 or a later version.

The margins should be at least 1.50 inches for the binding edge and 1.0 inches for all others.

In the top left portion of each table/listing, the *protocol number* will be presented. On the next line, a *table/listing number* followed by the *title* of the table/listing and *analysis population* information will be displayed. Horizontal lines will appear after the column heading of the table/listing. *Footnotes* will be put under the main body of text at the bottom of the page. The source listing number will be displayed for all tables. The *SAS program name* will appear in the bottom left corner in a string, and the *page number* will appear in the top right corner of each table/listing. The *date and time of creation* of the table/listing will appear in the bottom left corner under to the SAS program name line.

Courier New 8-point font will be used for all tables and listings. Usually, a landscape layout is suggested for both tables and listings, but it is not mandatory. Any date information in the listing will use the date9. format, for example, 07MAY2002.

Shells for tables and listings are provided in a separate Mock-Up TFL document.

APPENDIX 1: SCHEDULE OF ASSESSMENTS

Table 1: Schedule of Assessments (SoA)

	Screening	Baseline	Treatment Period														End of trial	
Visit No. ¹	1	2 ³	3	4	5 ³	6	7	8	9	10 ^{2b}	11	12	13	14	15	16 ³	17	18
Week (weeks unless indicated)	-4 to -2 (Day -28 to -14)	-1 (Day-7 to -3)	0 (Day 0)	2 (+1)	4	8 ⁴ (±1)	12 (±2)	16 (±2)	20 (±2)	24 (±2)	28 (±2)	32 (±2)	36 (±2)	40 (±2)	44 (±2)	48 (±1)	52 (±2)	4 weeks after last dose ±1 week
General																		
Informed consent	X																	
Inclusion and Exclusion criteria	X	X																
Demographics	X																	
Medical history	X																	
Concomitant medication	X	X	X	X	X	X	X	X	X	X	X	X	X	X	X	X	X	X
GI health history	X	X	X															
Metabolic balance evaluation (see Table 2 for detailed schedule)		X			X												X	
Safety																		
Colonoscopy or colonography ^{5,7}	X									X ⁶							X ²³	
Physical examination ⁸	X	X			X					X							X	X
12-lead ECG ⁸	X	X			X					X							X	X

	Screening	Baseline	Treatment Period														End of trial	
Visit No. ¹	1	2 ³	3	4	5 ³	6	7	8	9	10 ²⁶	11	12	13	14	15	16 ³	17	18
Week (weeks unless indicated)	-4 to -2 (Day -28 to -14)	-1 (Day-7 to -3)	0 (Day 0)	2 (+1)	4	8 ⁴ (±1)	12 (±2)	16 (±2)	20 (±2)	24 (±2)	28 (±2)	32 (±2)	36 (±2)	40 (±2)	44 (±2)	48 (±1)	52 (±2)	4 weeks after last dose ±1 week
Vital signs (blood pressure, heart rate, axillary temperature) ⁸	X	X	X	X	X	X	X	X	X	X	X	X	X	X	X	X	X	X
Body weight and height ⁹	X	X	X	X	X	X	X	X	X	X	X	X	X	X	X	X	X	X
Adverse events ¹⁰	X	X	X	X	X	X	X	X	X	X	X	X	X	X	X	X	X	X
Investigator narrative		X		X	X	X	X	X	X	X	X	X	X	X	X	X	X	X
Telephone contact ¹¹	X		X															
Laboratory																		
Clinical chemistry incl. liver enzymes, hematology, hemostasis, urinalysis (dipstick)	X	X		X	X	X	X	X	X	X	X	X	X	X	X	X	X	X
Serum pregnancy test premenopausal women	X	X		X	X	X	X	X	X	X	X	X	X	X	X	X	X	X
Blood samples for PK ¹²				X	X		X			X		X		X		X	X	X
Blood sample for citrulline ¹²		X		X	X		X			X		X		X		X	X	X
Blood sample for ADA ¹²		X		X	X		X			X				X		X		X ¹³

Visit No. ¹	Screening	Baseline	Treatment Period														End of trial	
	1	2 ³	3	4	5 ³	6	7	8	9	10 ²⁶	11	12	13	14	15	16 ³	17	18
Week (weeks unless indicated)	-4 to -2 (Day -28 to -14)	-1 (Day-7 to -3)	0 (Day 0)	2 (+1)	4	8 ⁴ (±1)	12 (±2)	16 (±2)	20 (±2)	24 (±2)	28 (±2)	32 (±2)	36 (±2)	40 (±2)	44 (±2)	48 (±1)	52 (±2)	4 weeks after last dose ±1 week
HIV and hepatitis test	X																	
Post-PS volume reduction safety evaluations ¹⁴					X	X	X	X	X	X	X	X	X	X	X	X	X	
Efficacy																		
Prescribed PS volume, composition, days per week	X	X	X	X	X	X	X	X	X	X	X	X	X	X	X	X	X	X ¹⁵
Define and confirm drinking menu ¹⁶	X	X																
Patient Reported Outcome (PRO) questionnaires ²		X			X		X			X			X				X	X
Change in Eating/Appetite		X		X	X	X	X	X	X	X	X	X	X	X	X	X	X	X
Urine sample for sodium analysis (from sample taken during 48-hour urine collection, balance period) ¹⁶		X ¹⁷		X	X ¹⁷	X	X	X	X	X	X	X	X	X	X	X ¹⁷	X	
DEXA Scan		X			X					X						X		
Gastroduodenoscopy	X									X ⁶						X ²³		
Trial Medication and																		

	Screening	Baseline	Treatment Period														End of trial	
Visit No. ¹	1	2 ³	3	4	5 ³	6	7	8	9	10 ²⁶	11	12	13	14	15	16 ³	17	18
Week (weeks unless indicated)	-4 to -2 (Day -28 to -14)	-1 (Day-7 to -3)	0 (Day 0)	2 (+1)	4	8 ⁴ (±1)	12 (±2)	16 (±2)	20 (±2)	24 (±2)	28 (±2)	32 (±2)	36 (±2)	40 (±2)	44 (±2)	48 (±1)	52 (±2)	4 weeks after last dose ±1 week
Diary																		
Hand out subject e-diary	X																	
Subjects complete diary prior to the visit		X		X	X	X	X	X	X	X	X	X	X	X	X	X	X	
Review all subject diary information since last visit		X		X	X	X	X	X	X	X	X	X	X	X	X	X	X	
SC injection of IMP at site			X	X	X	X	X	X	X	X	X	X	X	X	X	X		
Instruct subject in IMP handling at home and assess self-administration capability ¹⁸			X															
Dispense IMP			X	X	X	X	X	X	X	X	X	X	X	X	X	X		
Return home administered IMP vials to site				X	X	X	X	X	X	X	X	X	X	X	X	X	X	
																		
																		

	Screening	Baseline	Treatment Period														End of trial	
Visit No. ¹	1	2 ³	3	4	5 ³	6	7	8	9	10 ²⁶	11	12	13	14	15	16 ³	17	18
Week (weeks unless indicated)	-4 to -2 (Day -28 to -14)	-1 (Day-7 to -3)	0 (Day 0)	2 (+1)	4	8 ⁴ (±1)	12 (±2)	16 (±2)	20 (±2)	24 (±2)	28 (±2)	32 (±2)	36 (±2)	40 (±2)	44 (±2)	48 (±1)	52 (±2)	4 weeks after last dose ±1 week
[REDACTED]		■			■					■						■		
[REDACTED]		■			■					■						■		
[REDACTED]	■									■						■		
[REDACTED]	■									■						■		
[REDACTED]		■			■					■						■		
[REDACTED]		■			■					■						■		
[REDACTED]		■			■					■						■		
[REDACTED]		■			■					■						■		

ADA, anti-drug antibodies; AE, adverse event; AESI, adverse event of special interest; DEXA, dual-energy X-ray absorptiometry; ECG, electrocardiogram; EOT, end of trial; GI, Gastrointestinal; HIV, human immunodeficiency virus; IMP, investigational medicinal product; LTE, long-term safety and clinical outcomes extension trial; [REDACTED], PGIC, patient global impression of change; PGIS, patient global impression of severity; PGI-PSI, patient global impression of parenteral support impact; PGI-SPS, patient global impression of satisfaction with parenteral support; PGI-TS, patient global impression of treatment satisfaction; PK, pharmacokinetics; PRO, patient reported outcomes; PS, parenteral support, [REDACTED]; SBS-IF-CIC-QOL, Short Bowel Syndrome with Intestinal Failure and Colon-in-Continuity Quality of Life questionnaire; SBS-IF-TI-QOL, Short Bowel Syndrome with Intestinal Failure - Treatment Impacts - Quality of Life questionnaire; SC, subcutaneous; [REDACTED]

1. If at any visit the subject shows signs of significant fluid overload, leading to clinical decompensation, the Investigator should consider PS reduction. An AESI of fluid overload must be reported. In all cases this reduction must be discussed with the medical monitor either before or after reduction.

[REDACTED]

Table 2: Schedule of Assessments for Metabolic Balance Periods (Visits 2 (Baseline), 5, and 16)

Procedure	Metabolic balance period				
	Day 1	Day 2	Day 3	Day 4	Day 5
Admission to hospital	X (at least 16 h prior to MB samples collection start)				
Hospital discharge					X
Confirmation of eligibility ¹	X Baseline only				X Baseline only
Review all subject diary information since last visit	X				
Adverse events	X	X	X	X	X
Concomitant medication	X	X	X	X	X
Investigator narrative	X				
GI health history	X				
Physical examination	X				
12-lead ECG	X				
Vital signs (blood pressure, heart rate, axillary temperature) ²	X	X	X	X	X
Clinical chemistry	X				
Hematology	X				
Hemostasis	X				
Urinalysis	X				
Pregnancy test (premenopausal women)	X				
Citrulline blood sample	X				
Blood samples for PK (Visits 5 and 16) ¹		Pre-dose (within 30 min prior to dosing)	24 h (±2 h), 30 h (±2 h),	48h (±2 h),	72 h (±2 h),
Blood sample ADA, nAb	X				

	Metabolic balance period				
Procedure	Day 1	Day 2	Day 3	Day 4	Day 5
Fasting	X (start 22:00 ±30 min)	X (until start of MB collections)			
Urinate & defecate – prior to MB collection start ¹		X (-30 min)			
Urinate & defecate – end of MB period					X (-30 min)
Body weight ²	X	X	X	X	X
Start of MB collection ²		X Time of IMP ³ (+15 min)			
Collection of urine		X	X	X	X
Collection of feces		X	X	X	X
Collection of duplicate food and drinks		X	X	X	X
End of MB collection					72 h from start (±1 h)
Change in appetite	X				
Confirm drinking menu	X Baseline only				
Adhere to agreed upon drinking menu		X	X	X	X
Define baseline PS type, volume, content	X Baseline only				
Fixed baseline PS type, volume and content (baseline & Visit 5)		X	X	X	X
DEXA Scan		X ⁴			
Patient reported outcomes (PRO)		X (13:00-18:00)			

Procedure	Metabolic balance period				
	Day 1	Day 2	Day 3	Day 4	Day 5
Bristol Stool Form Scale and Frequency of bowel movement		X	X		
IMP administration (Visits 5 and 16)		X			
Dispense IMP (Visits 5 and 16)					X
[REDACTED]					

ADA, anti-drug antibodies; [REDACTED]; DEXA, dual-energy X-ray absorptiometry; ECG, electrocardiogram; GI, gastrointestinal; IMP, investigational medicinal product; nAb, neutralizing antibody; PK, pharmacokinetics; PRO, patient reported outcomes; PS, parenteral support; MB, metabolic balance; [REDACTED]; [REDACTED]; [REDACTED]

1. At the first MB period only, confirmed of Screening eligibility to be confirmed on Day 1 and confirmation of inclusion criteria 12 and 13 to be confirmed on Day 5.
2. The activities should be performed in the following sequence on Days 2-5: AE collection, weight, vital signs, pre-dose PK sample (Visits 5 and 16 only), defecate/urinate, IMP administration (Visits 5 and 16 only), start of 72-hour collection of urine, feces and food. Body weight and vital signs will be measured on Day 1 at any time, on Day 2 after defecation but before IMP administration, and on subsequent days at the same time as on Day 2 ± 1 h.
3. Visits 5 and 16 MB periods only.
4. Same timing across all MB periods with regard to PS infusion and time of day based on first MB period ± 2 h (see Section 5.2 of the protocol for more details).

[REDACTED]

[REDACTED]

